3.1.5 Safety

Concomitant medications, laboratory tests, and safety assessments including adverse events (AEs), Columbia-Suicide Severity Rating Scale (C-SSRS), Questionnaire for -Impulsive-Compulsive Disorders in Parkinson's Disease-Rating Scale (QUIP-RS), and vital signs (including orthostatic assessment) will be performed at all visits. A 12-lead electrocardiogram (ECG) will be conducted at Screening (Visit 1) and then at Baseline (Visit 2) and every visit thereafter; three consecutive 12-lead electrocardiogram (ECG) evaluations will be conducted before and 1 to 2 hours after the study treatment dose administered at the clinic (approximate C_{max}).

All AEs and concomitant medications will be recorded from Screening (Visit 1) until the last study visit. During all telephone contacts, patients will be asked to provide details on AEs and concomitant medication changes.

Details of all safety assessments performed during the study are provided in [Section 6, Table 4](#).

3.1.6 Pharmacokinetics

PK sampling for levels of pridopidine and its metabolite TV-45065 will be performed at the time points noted in the schedule of assessments ([Table 4](#)) (approximately 1 hour before and 1 to 2 hours after the PM pridopidine dose). When coincident with ECG monitoring, PK samples will be collected within 30 minutes after the ECG recording.

Details of all PK assessments performed during the study are provided in [Section 6, Table 4](#).

3.1.7 Pharmacogenetic and Plasma Biomarker Substudy

Patients will sign a separate informed consent form (ICF) for pharmacogenetic and plasma biomarker assessments before any are performed. Participation in this assessment is voluntary and patients can opt out at any time.

Sampling analyses for DNA extraction will be performed only once during the study at Screening (Visit 1) or Baseline (Visit 2). Plasma samples for potential biomarkers research will be collected at the time points noted in the schedule of assessments ([Table 4](#)).

3.1.8 Rationale of Study Design

A randomized, double-blind, placebo-controlled, three-arm, parallel-group study design was chosen for this Phase 2B study to allow comparison of safety, tolerability, efficacy, and PK for 2 dosages of the study treatment versus the placebo control arm.

The starting dose was chosen based on prior clinical experience demonstrating that the initiation of treatment with a pridopidine dose of 67.5 mg BID in healthy volunteers (135 mg/day, multiple-ascending dose study) was well tolerated, and that a dose of 45 mg BID (90 mg/day) has a safety profile similar to that of placebo as seen in HD patients.

Pridopidine has the potential to fulfill an unmet need in the treatment of dyskinesia based on preclinical studies that support the ability of pridopidine to reduce LID without causing an adverse effect on Parkinsonian symptoms and in clinical studies of patients with HD involving pridopidine at doses up to 112.5 mg BID, that demonstrate an overall good safety and tolerability profile.

The variables used for assessing PK, safety and efficacy are standard measures in clinical study in PD patients.

4 Patient Selection and Withdrawal Criteria

4.1 Selection of Study Population

Approximately 135 patients will be enrolled at 42 sites in the US (45 randomized patients in each treatment group). Patients will be assigned to study treatment only if they meet all the inclusion criteria and none of the exclusion criteria.

4.1.1 Inclusion Criteria

Patients may be included in the study only if they meet all of the following criteria:

1. Male or female patients between 30 and 85 years of age, inclusive
2. Signed an IRB-approved ICF
3. Diagnosis of PD consistent with the UK Parkinson's Disease Society (UKPDS) Brain Bank Clinical Diagnostic Criteria
4. Hoehn and Yahr Stage 4 or less in the "ON" state such that the patient can complete the study assessments
5. Documentation of LID by the investigator
6. A score of 3 on 2 elements of the Unified Dyskinesia Rating Scale (UDysRS) part 4 – Disability Scale
7. Using the three consecutive 24-hour "ON/OFF" home diaries completed prior to Baseline (Visit 2), at least two half-hour time periods one between 8:00 AM and 5:00 PM of each 24-hour period are indicated as "ON with dyskinesia"
8. Patient and/or study partner must demonstrate during the screening period an ability to keep accurate home diary entries of PD symptoms ("ON, OFF, and dyskinesia") with >75% concordance with the study rater. During the 4-hour concordance testing, patient must experience all motor states: "ON", "OFF" and at least one period of "ON with dyskinesia"
9. Patients who are stable on a total daily dose of ≤ 200 mg amantadine must be off this treatment at least 4 weeks prior to the assessment of UDysRS part 4, the concordance testing and the completion of the three consecutive 24-hour "ON/OFF" home diaries which are performed during screening
10. All anti-PD treatments are stable for at least 28 days prior to Baseline (Visit 2), including a levodopa preparation administered no less than three times daily, with the same dosing regimen during the 12-week maintenance study treatment period

11. If taking allowed antidepressant or antipsychotic medication, must be on a stable dose for at least 28 days prior to Baseline (Visit 2) and must be kept constant during the study
12. Any other routine and allowed prescription/nonprescription medications and/or nutritional supplements taken regularly must be at stable dosages for at least 28 days prior to Baseline (Visit 2) and remain during study participation
13. Willing and able to comply with study requirements
14. Approval for entry into the study by an independent EAC (see [Section 6.10](#))

4.1.2 Exclusion Criteria

Patients meeting any of the following criteria will be excluded from the study:

1. Diagnosis of atypical Parkinsonism
2. History of exclusively diphasic, “OFF” state, myoclonic, or dystonic dyskinesia without peak-dose choreiform dyskinesia
3. Treatment with dopamine blocking drugs (e.g., neuroleptics, Reglan® [metoclopramide])
4. History of surgical intervention related to PD (e.g., deep brain stimulation, carbidopa-levodopa intra-enteral suspension [CLES; Duopa™])
5. Presence of clinically significant orthostasis symptoms, e.g., arterial hypotension
6. Clinically significant medical, surgical, psychiatric, or laboratory abnormality in the judgment of the investigator
7. Any physical impairment that by the judgment of the investigator impairs the ability of the patient to complete study assessments
8. History of severe depression, psychosis or hallucinations within 6 months prior to Screening (Visit 1)
9. History of active suicidal ideation as assessed by the investigator or measured by a score of 4 (Active Suicidal Ideation with Some Intent to Act, without Specific Plan) or 5 (Active Suicidal Ideation with Specific Plan and Intent) on the Columbia-Suicide Severity Rating Scale (C-SSRS) within 6 months prior to Screening (Visit 1), or suicidal attempt within 5 years prior to Screening (Visit 1)

10. History of cancer within 5 years prior to Screening (Visit 1), with the following exceptions if adequately treated: non-melanomatous skin cancers, localized bladder cancer, non-metastatic prostate cancer or in situ cervical cancer
11. Presence of cognitive impairment, as evidenced by a Mini Mental State Examination (MMSE) score of <24 not including dementia at Screening (Visit 1)
12. A prolonged Fridericia-corrected QT (QTcF) interval (defined as a QTcF interval of >450 msec) at Screening (Visit 1)
13. Clinically significant heart disease at Screening (Visit 1), defined as follows:
 - (i) significant cardiac event within 12 weeks prior to Baseline (Visit 2) (e.g., admission for myocardial infarction, unstable angina, or decompensated heart failure), angina pectoris or episode of congestive heart failure with symptoms > grade 2 New York Heart Association classification, or presence of cardiac disease that in the opinion of the investigator increased the risk of ventricular arrhythmia
 - (ii) history of complex arrhythmia (multifocal premature ventricular contractions, bigeminy, trigeminy, ventricular tachycardia) that was symptomatic or required treatment (Common Terminology Criteria for Adverse Events grade 3), symptomatic or uncontrolled atrial fibrillation despite treatment, or asymptomatic sustained ventricular tachycardia
 - (iii) symptomatic bradycardia, sick sinus syndrome or atrioventricular block greater than first degree in the absence of a functioning pacemaker
 - (iv) unexplained syncope
 - (v) Brugada syndrome
 - (vi) hypertrophic cardiomyopathy
14. History of congenital long QT syndrome or a first degree relative with this condition
15. History of epilepsy or of seizures within 5 years prior to Baseline (Visit 2)
16. History of clinically significant deficit from stroke or transient ischemic attack within 6 months prior to Screening (Visit 1)
17. Serum potassium, magnesium and/or calcium levels outside of the central laboratory's reference range at Screening (Visit 1) visit and considered clinically significant by the investigator. Repeat testing is allowed (up to a maximum of three tests) if required to establish whether values are within normal range or not clinically significant
18. Use of all oral cannabinoids (including all preparations containing any cannabinoids, prescribed oral medical marijuana and oral cannabidiol) with the exception of topical formulations of cannabidiol, within 28 days prior to Baseline (Visit 2)

19. Use of medications (within the last 6 weeks prior to Baseline [Visit 2]) that have been demonstrated to prolong the QT interval, or any patients who may require such medications during the course of the study such as but not limited to prohibited antipsychotic medications, tricyclic antidepressants and/or Class I antiarrhythmic (see [Table 3](#) and [Section 5.10.1](#))
20. Treatment with apomorphine during the 28 days prior to Screening (Visit 1)
21. Body surface area (BSA)-adjusted creatinine clearance <50 mL/min/1.73 m² at Screening (Visit 1), calculated using the Cockcroft-Gault equation: $[(140 - \text{age}) \times \text{mass} (\text{kg}) \times [0.85 \text{ if female}]] / [72 \times \text{serum creatinine} (\text{mg/dL}) \times \text{BSA} (\text{m}^2)] / 1.73$. Repeat testing is allowed once, if clinically appropriate
22. Alcohol and/or drug abuse within 6 months prior to Screening (Visit 1), as defined by Diagnostic and Statistical Manual – Fifth Edition Text Revision Criteria for Substance Abuse
23. Females who are pregnant or breastfeeding
24. Sexually active female patients, who are not surgically sterile or at least 2 years postmenopausal prior to Screening (Visit 1), and do not agree to utilize a highly effective hormonal method of contraception (an intrauterine device or vasectomized male partner is also acceptable), in combination with a barrier method, from Screening (Visit 1) through at least 4 weeks after the completion of study treatment
25. Male patients not using highly effective contraception or not agreeing to continue highly effective contraception through at least 90 days after the completion of study treatment
26. Known allergy to any ingredients of the study treatment or placebo (pridopidine, silicified microcrystalline cellulose, magnesium stearate)
27. Treatment with any investigational product within 30 days of Screening (Visit 1) or patients planning to participate in another clinical study assessing any investigational product during the study
28. Planned elective surgery during study participation

4.2 Withdrawal of Patients from Study Treatment and/or the Study

The duration of the study is defined for each patient as the date signed written informed consent is provided through the last safety follow-up visit at Visit 8. If a patient discontinues treatment, they will be encouraged to remain in the study and continue study visits and procedures for the full course of the study without receiving study treatment. Patients who withdraw from the

study before the Visit 7/ET visit and are not willing to continue study visits and procedures for the full course of the study will be asked, to undergo an ET visit that will include all evaluations that were intended to be performed at the final visit.

4.2.1 Reasons for Withdrawal/Discontinuation

Patients are free to withdraw from the study at any time and for any reason without prejudice. The investigator also has the right to withdraw a patient from the study if an intercurrent illness or AE occurred, if the patient did not cooperate, or for any reason concerning the health or well-being of the patient. The reasons for patients not completing the study will be recorded.

Among other reasons, a patient may be discontinued from the study treatment or the study if they meet any of the following stopping rules:

QTcF stopping rules

- QTcF >500 msec (based on the mean value from the triplicate ECG measurements)
- QTcF >480 msec with concurrent increase in QTcF >60 msec (Δ QTcF, based on the mean value from the triplicate ECG measurements) from Baseline (Visit 2)
- Patients with QTcF >480 msec or with an increase of QTcF >60 msec from Baseline (Visit 2) will return to the clinic within 48 to 72 hours for repeat evaluation of electrolyte levels and repeat triplicate ECGs to demonstrate reversibility of the effect on QTcF. Decision on discontinuation will be determined by EAC

Creatinine clearance stopping rule

Patients with an adjusted CrCL <50 mL/min/1.73 m² calculated by CrCL * BSA/1.73, where CrCL is calculated using the Cockcroft-Gault equation $[(140 - \text{age}) \times \text{mass (kg)} \times [0.85 \text{ if female}] / 72 \times \text{serum creatinine (mg/dL)}]$ at any time point after Baseline (Visit 2) will be requested to return to the clinic for an unscheduled visit 1 week later to repeat the CrCL test one more time for confirmation. If the repeated CrCL value is confirmed to be <50 mL/min/1.73 m², the patient will be discontinued from the study treatment.

The investigator will also withdraw a patient if Prilenia Therapeutics or regulatory authorities terminate the study. If a patient is discontinued because of an AE, the event will be followed until it has resolved.

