6.5.1.6 Suspected Unexpected Serious Adverse Reactions and Nonserious Adverse Events of Special Interest

The sponsor will promptly evaluate all SUSARs against cumulative product experience to identify and expeditiously communicate possible new safety findings to investigators, IRBs/IECs, and applicable health authorities based on applicable legislation.

To determine reporting requirements for single AE cases, the sponsor will assess the expectedness of these events using the study treatment investigator's brochure.

Prilenia Therapeutics will compare the severity of each SUSAR and the cumulative event frequency reported for the study with the severity and frequency reported in the applicable reference document.

Reporting requirements will also be based on the investigator's assessment of causality and seriousness, with allowance for upgrading by the sponsor as needed. All AEs will be evaluated with equal interest.

Events of discontinuation due to meeting the QTcF stopping rules (defined in [Section 4.2.1](#)) will be considered AEs of special interest.

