The patient must be in a supine position and resting for at least 5 minutes prior to each ECG measurement. Where applicable, ECG measurements should be taken prior to vital sign measurements and blood being drawn for clinical laboratory or PK evaluations. A qualified physician at the central ECG vendor will be responsible for interpreting the ECG and send results within 24 hours. However, every ECG should be reviewed immediately at site for the purpose of determining any gross abnormality (like new atrial fibrillation or QTcF prolongation) that might affect patient safety and not allow dosing. If the local ECG reading results at the site match any of the discontinuation criteria (see [Section 4.2.1](#)), the patient should stop taking study treatment until the central ECG reader's report is received. If the central reader does not report a QTcF interval that would lead to discontinuation according to the above, then the patient should restart study treatment. Any ECG finding that is judged by the investigator or the physician from the central ECG vendor as a clinically significant change (worsening) compared with a Visit 2 value will be considered an AE, recorded on the source documentation and transcribed onto the eCRF and monitored as described in [Section 6.5.1.4](#).

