7.3 Safety Endpoints

The following safety and tolerability endpoints will be evaluated:

Safety:

1. AEs occurring throughout the study
2. QTc parameters: absolute QTcF of >450 msec, >480 msec, and >500 msec, mean QTcF, change in QTcF >30 msec and <60 msec, or changes in QTcF >60 msec throughout the study
3. Clinical safety laboratory (clinical chemistry, haematology and urinalysis, vital signs (including assessment of orthostatic hypotension), physical and neurological examination, concomitant medications throughout the study
4. Change from Baseline (Visit 2) in suicidality as evaluated with the C-SSRS throughout the study
5. Change from Baseline (Visit 2) in impulse control disorder (ICD) as evaluated by the QUIP-RS throughout the study

Tolerability:

1. The number (%) of patients who complete the study treatment
2. The number (%) of patients who fail to complete the study treatment due to AEs
3. The number (%) of patients who fail to complete the study treatment due to QTcF and QT stopping rules, seizure or convulsions ([Section 4.2.1](#))

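### Protocol 4.2.1 does not require stopping study drug for a centrally confirmed QTcF above 500 msec (or above 480 msec with a rise above 60 msec), and its EAC sentence also covers these patients

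*Protocol*

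**What the plan says.** All stopping rules in protocol 4.2.1 sit under one lead-in: "a patient may be discontinued from the study treatment or the study if they meet any of the following stopping rules". Three QTcF bullets follow.

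- Bullet 1 is a threshold alone: "QTcF >500 msec (based on the mean value from the triplicate ECG measurements".
- Bullet 2 is also a threshold alone: above 480 msec together with a rise above 60 msec from Visit 2, again on the triplicate mean.
- Bullet 3 has an action: "Patients with QTcF >480 msec or with an increase of QTcF >60 msec from Baseline (Visit 2) will return to the clinic". That visit falls 48 to 72 hours later and covers electrolytes and a second set of triplicate ECGs. The bullet ends: "Decision on discontinuation will be determined by EAC".

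The creatinine clearance rule, under the same lead-in, supplies its own mandatory verb once the low value is confirmed: "the patient will be discontinued from the study treatment".

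Three other places refer back to these rules. Section 6.5.2 begins an interim hold with "If the local ECG reading results at the site match any of the discontinuation criteria": the patient stops drug until the central report arrives, and restarts if that report does not show a value warranting discontinuation. Section 6.5.1.6 classes "Events of discontinuation due to meeting the QTcF stopping rules" as adverse events of special interest. Section 7.3 counts patients who "fail to complete the study treatment due to QTcF and QT stopping rules".

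**The concern.** A stopping rule should tell the site what to do at the threshold. For the two upper tiers, 4.2.1 gives permission to discontinue and nothing firmer. Bullet 3 then appears to pass the decision to the EAC. The EAC's described job is eligibility review (6.5.8, 6.10), and 6.5.8 describes its members as independent neurologists. The body that includes a cardiologist is the DSMB (6.6).

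This is the main cardiac safety rule of a trial whose upper dose, 150 mg BID, exceeds the 112.5 mg BID that section 1.2.1.1 gives as the highest dose tested in humans. Two sites could act differently on the same confirmed value of 505 msec and both be following the protocol.

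**Working it through.** The plan has no figure to reproduce here. The check is of logic and wording.

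**Step 1: do bullets 1 and 2 fall inside bullet 3?** Write Q for the on-treatment triplicate-mean QTcF and D for its change from Visit 2.

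- Bullet 1: Q > 500
- Bullet 2: Q > 480 and D > 60
- Bullet 3: Q > 480 or D > 60

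Q > 500 implies Q > 480, so bullet 1 lies inside bullet 3. Meeting both limbs implies meeting at least one, so bullet 2 does too. A check over whole-number values of Q from 350 to 600 and D from −100 to +200 found 0 points in bullet 1 or 2 outside bullet 3.

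**Step 2: worked cases.** The 450 msec starting value in A and C is the highest that exclusion 12 allows at Screening. Using it as the Visit 2 value is an assumption.

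| Case | Visit 2 | On treatment | Change | Bullet 1 | Bullet 2 | Bullet 3 |
|---|---|---|---|---|---|---|
| A | 450 | 505 | 505 − 450 = 55 | yes | no | yes |
| B | 420 | 485 | 485 − 420 = 65 | no | yes | yes |
| C | 450 | 490 | 490 − 450 = 40 | no | no | yes |

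Patient C belongs in bullet 3 alone. Patients A and B are in an upper tier and also under the EAC sentence.

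**Step 3: does any section make stopping mandatory for A or B?**

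- 4.2.1 lead-in: permissive.
- 4.2.1 bullets 1 and 2: no action stated. The creatinine rule shows that the authors could override the lead-in with a mandatory verb.
- 4.2.1 bullet 3: a return visit, then an EAC decision.
- 6.5.2, local reading matches a criterion: drug is held. The restart sentence covers only a central report that does not bear the value out. Action on confirmation is left to inference, and the inference leads back to 4.2.1.
- 6.5.2, local reading misses the value: no hold is triggered. When the central report arrives, only 4.2.1 applies.
- 6.5.1.6 and 7.3: these classify and count discontinuations and do not order them.

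No section requires stopping for a centrally confirmed value in bullet 1 or 2.

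**Step 4: dosing for patient C.** After central confirmation, neither section clearly says whether drug is held until the repeat ECG and the EAC decision. This is a smaller gap.

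**The case against.** The strongest reply is that 6.5.2 already does most of the work. A patient whose value above 500 msec is seen locally and confirmed centrally is off drug, and the text gives no route back on. Every ECG is to be reviewed at the site at once, and central results are due within 24 hours. The investigator may also withdraw any patient for health reasons (4.2.1), and the DSMB could discontinue individual patients if a significant high-dose concern emerged (6.6), although SAP 9.3 records that no formal meeting took place. This stands, and it narrows the gap to two things: the missing instruction on confirmation, and the value the local reader missed.

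A reader might infer that bullet 3 gives the upper tiers an instruction that conflicts with stopping. The documents do not support that. Stopping drug and returning for electrolytes and ECGs are compatible, and patients in the upper tiers need the recheck. The only real tension is whether the EAC sentence governs them.

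A reader might also infer from 6.5.1.6 and 7.3 that mandatory stopping was plainly intended. Those sections fit a discretionary rule equally well. Only 6.5.2 leans towards mandatory stopping.

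**Conclusion.** The point holds as a gap in a safety rule. On its wording, 4.2.1 permits but does not require discontinuation for a centrally confirmed value in bullet 1 or 2, and it also places that decision with the EAC. Section 6.5.2 reduces the exposure without closing the gap.

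It would go too far to conclude that the protocol keeps patients on drug above 500 msec, or that anyone was exposed in this way. The hold in 6.5.2 argues against the first, and nothing in the documents shows the second.

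The size is small. SAP 9.3 puts enrolment below 30 subjects. Only the 150 mg BID arm exceeds prior human dosing; the 100 mg BID arm does not. The efficacy analysis is unaffected. The overlap follows from the thresholds alone. The rest depends on reading 4.2.1 and 6.5.2 as printed, without the study manual or DSMB charter, which might say more.

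**What to change.** Make two edits in 4.2.1.

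(a) Give bullets 1 and 2 an action: *Patients whose centrally read triplicate-mean QTcF exceeds 500 msec, or exceeds 480 msec with a rise of more than 60 msec from Visit 2, will be discontinued from study treatment.* Naming treatment rather than the study fits section 4.2, which encourages such patients to continue visits.

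(b) Keep the 48 to 72 hour electrolyte and triplicate ECG visit for every patient above 480 msec or with a rise above 60 msec, and limit only the last sentence of bullet 3: *For patients who meet neither criterion above, the EAC decides on discontinuation.* Bullet 3 as a whole should not be restricted to patients outside bullets 1 and 2. That would take the only timed recheck away from those at highest risk; the general rule of following an adverse event to resolution sets no timing.

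As an option, state whether drug is held for a confirmed value in bullet 3 only until the EAC decides, and align the restart sentence in 6.5.2.

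In the worked cases, A and B would then be discontinued and rechecked, and C would be rechecked with an EAC decision.

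The cost is some lost discretion: a reversible prolongation in the upper tiers, for example from an electrolyte disturbance, would end study treatment. The change alters a stopping rule, so it needs a protocol amendment with IRB/IEC approval (11.2.1). It adds no procedures, data or analyses. Since the study was terminated early, the main use of the corrected wording is in any later protocol that reuses this text.
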